Research assessments will occur at baseline during hospitalization and 30 days after discharge from the hospital (“30-day follow-up”). Both assessments will ideally be in-person visits, with research staff administering assessments in an interview format. Point-of-care urine drug testing using Alere 14 Panel Drug Test iCup DX or equivalent will be administered at the 30-day follow-up visit only. Study data (including screening, assessment, urine drug testing results) will only be recorded for research purposes and will not be shared with clinical providers outside of the study team (unless there are imminent safety concerns). Participants will be reimbursed \$60 for the baseline visit and \$60 for the 30-day follow-up visit, plus another \$20 at the 30-day follow-up visit if a urine drug test is provided. This reimbursement for study participation will be provided to both study arms (MIAPP and control arm). At the 30-day follow-up visit, participants will return any study-provided smartphones, if utilized. Data extraction for secondary outcomes will occur after 180 days, which will encompass the 30-, 90-, and 180-day outcome timepoints we will report. These secondary outcomes will include outpatient visits/medications, hospital readmissions, and emergency department visits and will be obtained through partnership with WA State DSHS RDA. Data will be collected for patients who are enrolled in the pilot RCT (Aim 1), as well as for a larger, historical, observational cohort of HMC patients who initiated

treatment with buprenorphine between 2019 and 2021 (Aim 2). This will ensure the feasibility of collecting outcomes for a larger sample size and provide estimates of rates of healthcare utilization that can be used to power a larger clinical trial.

Eligibility

Inclusion Criteria:

- ≥ 18 years old
- Admitted to HMC on any inpatient service
- Initiated on sublingual buprenorphine for OUD while in the hospital or at the time of discharge and planning to continue outpatient
- Used methamphetamine within the past 30 days (any route of administration or frequency), per patient self-report at screening
- Willing to be randomized to MIAPP intervention or control condition
- Willing and able to use a smartphone (study can provide) and work with patient navigator
- Discharge setting does not preclude the use of video-DOT (i.e., nursing home, inpatient psychiatry, etc.)

Exclusion Criteria:

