Participants will sign two copies of the informed consent form. Prior to having the participants sign the informed consent the research staff will check to make sure that the most current draft of the informed consent form is being used. After the participant has signed, the research staff will review the forms to ensure that they are correctly signed and dated. One copy will be sent home with the participant and the other will be stored in a locked cabinet with the research study team. This form should never be stored with participant study data.

HIPAA Authorization Form

Research staff must have the study participant complete and sign four HIPAA Authorization Forms. Two UW HIPAA Authorization forms and two Washington State HIPAA forms. One of each forms will be given to the participant and the others will be stored in a locked filing cabinet, along with the signed consent form. This form should never be stored with participant study data.

Release of Information (ROI) Form – for discharge to outpatient treatment outside of UW system

Data will be collected on the location where continued buprenorphine treatment is planned via self-report during the screening assessment. If the patient is determined to be eligible at the time of screening, provides informed consent to participate in the study, and there is ambiguity from the patient self-report during screening regarding discharge date and location, research staff should connect with the Addiction Consult Service before the patient is discharged from the hospital to clarify where the participant will be planning to continue outpatient buprenorphine treatment. Two ways the research staff will connect with ACS staff will be by attending the morning rounds meeting which occur daily at 8:30am and through communicating via EHR staff messages within EPIC. Once the discharge location is determined and if the location is outside of the UW system, then the research staff member will fill out the necessary information in the Release of Information form, print the form and bring the copy to the participant in the hospital, and ask the participant to sign the form to obtain records. This process will need to be done for all participants regardless of which study condition they are assigned to.

Additionally, please note that this information on planned date and location of discharge for outpatient buprenorphine treatment will also need to be entered and/or updated in three places:

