Enrolled participants and their information are stored on the Excel database form “Enrolled participants.” This form tracks each visit including the research visit dates for each visit and payment verification tracking. It also logs contact information, if they borrowed a study phone and when it should be returned, etc. This form is also used as the cross-linking file that connects the participant’s MIAPP screening ID, MIAPP study ID, and, if randomized to MIAPP arm, Scene Health patient ID.

The following data elements will be tracked under the “Enrolled participants” tab of the Excel tracking database after enrollment:

- Screening ID
- Study ID
- Date enrolled in study
- Initials of staff member who enrolled participant
- Scene Health patient ID
- Contact information: phone, email, address, etc. (from [Participant Locator Form](#))
- Date of hospital discharge per self-report at screening, or EHR abstraction
- Location of clinic for discharge to outpatient buprenorphine treatment, per self-report at screening or per EHR review by research staff, or per ACS staff if ambiguity in self-report or EHR.
- Planned 30-day follow-up visit date (ideally schedule with participant before leaving the hospital, but if not possible the participant may be contacted after discharge to schedule the visit)
- follow-up visit status (completed / not completed)
- Money dispersed for BL and FU visits and FU urine test, etc.
- Credit card number of distributed PEX card for video upload incentives (if applicable and randomized to PN+mHealth arm)

Follow-Up Assessments

Follow-up Research Appointment (30 days post-discharge)

At the final visit, participants will complete a research interview and have the option to complete a urine drug test. The research interview will include questions for feedback on study experience, and satisfaction with the application (for MIAPP condition only). We will query patients at the 30-day follow-up visit to determine whether they have successfully engaged in outpatient treatment, which included medications, and we will obtain medical records from the setting they report receiving treatment from to substantiate. If patients are unable to complete a 30-day follow-up visit in person, we will obtain this

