information over the phone. Similar to the baseline assessment, the follow-up assessment will be completed via interviews with research staff, with the staff directly entering participants' responses into REDCap. A participant should be scheduled to complete the follow-up visit 30 days after discharge from hospital (or longer). These can be completed up to 90 days after discharge, if necessary. Ideally, they will be completed as close to 30 days as possible, but no less than 28 days after discharge.

Participants who were loaned phones for use during the study will be expected to return phones (and accessories- charger, case) at the final research visit. The following study checklist, that is provided at the end of the study assessment in REDCap and on paper, should be reviewed and checked to ensure all study closeout tasks are completed with the participant or after the final visit is completed.

- Retrieved study provided phone from participant, if possible
- Incentive receipt form signed by participant, physical copy with research staff
- TLFB form completed during visit, physical copy with research staff
- UDT form completed during visit, physical copy with research staff
- Entered follow-up assessment data into REDCap
- Entered in final visit tracking data into Excel database under "Enrolled Participants."

Data from Self-Report Buprenorphine Adherence Timeline Follow-back

Self-Reported OUD medication adherence will be assessed at the final visit and is determined by using a monthly calendar and an approved study timeline follow back process. Research staff will work with participants to document their total daily amount of buprenorphine and determine if they adhered to that daily amount every day for the 30 days after their hospital discharge date. This should be completed on paper and research staff person should note the participant study ID on the paper form. The calendar form will need to be printed prior to the final visit and brought to the visit, and the assessor should mark the date that the participant was discharged from the hospital at the top of the form. Additional instructions on the TLFB procedures will be provided within the REDCap final assessment. The paper forms should be stored in a locked filing cabinet within a folder that matches the study ID.

Data from Urine Drug Test

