Participants in the MIAPP + TAU arm can receive up to \$660 (\$140 for research assessments previously stated + \$520 financial incentives). Financial incentives will be provided for linking to outpatient buprenorphine programs and documenting daily medication adherence. Patients will receive a one-time reward of \$70 for linkage to an outpatient buprenorphine clinic, as evidenced by medication refill by outpatient provider (either demonstrated by medical records or patient providing a video of showing medication script or package/bottle), and \$15 for submitted video documenting daily adherence to buprenorphine (one reward available per day, for days 1-30 after hospital discharge). Reimbursements and incentives may be deposited by the Patient Navigator (or Research Coordinator if Patient Navigator is unavailable) onto a reloadable debit card, which research staff will add funds to throughout the study using an online account dashboard. We will use a reloadable prepaid debit card system that does not require participants to have a bank account. If necessary, the Research Coordinator/Patient Navigator will disburse cash to the participant in replacement of the reloadable debit card. Patients must meet study staff at Harborview Medical Center or Pat Steele Building to receive their funds. Research staff should strive to administer rewards as soon as possible to maximize reinforcement (ideally, the same day the videos were submitted or linkage was confirmed), and payments should be dispersed no more than 3-4 days after a video is submitted/confirmation of linkage has occurred.

Partial or prorated payments will not be offered, as we anticipate that in nearly all cases participants will either fulfill each activity (e.g., 30-day post-discharge visit, urine test, linkage to outpatient buprenorphine clinic, etc.) or not complete it at all. Therefore, we will offer full payment even if an activity is only partially completed (e.g., if a participant partially completes a 30-day post-discharge visit but leaves before it is fully completed, the participant will still receive the full payment for that activity).

It is important that research staff track this and document that the participant did in fact receive their payment, along with information about the payment that was issued (e.g., type of incentive, gift card serial numbers).

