Descriptive statistics will be calculated for all baseline variables; variables will be assessed for any differences between the two randomized arms using chi-square tests, t-tests, or the Mann-Whitney U test depending on the distributions. Baseline variables that differ between the two arms and potentially confound tests of intervention effects will be included in analyses as covariates. This study will use an intent-to-treat analysis including all subjects according to their randomized assignment, regardless of their follow-up status and their level of compliance with intervention components. The investigators will provide regular written reports to the Data Safety Monitoring Board including outcome data by the unblinded treatment group.

Primary Outcome Analyses

We hypothesize that participants randomized to MIAPP + treatment as usual compared to treatment as usual alone will be more likely to link to outpatient treatment with medications for OUD within the 30 days of hospital discharge. To evaluate the primary hypothesis, we will use modified Poisson regression analysis (53) with robust standard errors to compare intervention arms on the proportion of participants who link to outpatient treatment with medications for OUD within 30 days of hospital discharge, while potentially controlling for any baseline variables that differ between the two groups as described above if they could confound the hypothesis test. The results of this analysis will be presented as the proportion of patients in each group who link to outpatient treatment and the (adjusted) risk ratio (RR, i.e., ratio of the two proportions) with a 95% confidence interval computed by exponentially transforming the coefficient of the treatment effect in the modified Poisson regression model. We will also report the difference between proportions with a 95% confidence interval, as recommended by CONSORT guidelines (54). The RR and difference are two different ways of quantifying the intervention effect that have meaningful clinical interpretations. Results from the Poisson regression will be used for primary interpretation and conclusions.

Secondary Outcome Analyses

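### The only stated route to 30-day linkage depends on reaching the participant, contact and proof differ by arm, and no visit-independent source is assigned to the primary outcome

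*Combined protocol and SAP*

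**What the plan says.** **How linkage is determined.** The method appears in one place, the section Follow-up Research Appointment (30 days post-discharge): "We will query patients at the 30-day follow-up visit to determine whether they have successfully engaged in outpatient treatment, which included medications". The same sentence adds that "we will obtain medical records from the setting they report receiving treatment from to substantiate". The telephone is the fallback: "If patients are unable to complete a 30-day follow-up visit in person, we will obtain this" information by phone. Visits may not take place before day 28, and "These can be completed up to 90 days after discharge, if necessary".

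**How it is analysed.** The Statistical Analysis Plan specifies an intention-to-treat analysis "including all subjects according to their randomized assignment, regardless of their follow-up status". It gives no operational definition of linkage, no order of precedence among sources, and no rule for a participant whose outcome is unknown.

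**What differs by arm.** Under Compensation, Research Reimbursements and Incentives, and Patient Navigation, only MIAPP participants have a navigator for 30 days after discharge, $15 per daily video, and $70 for proof of linkage. That proof is "either demonstrated by medical records or patient providing a video of showing medication script or package/bottle". Under Baseline Visit, the navigator may be the same person as the research staff member. Payment for research visits is equal in both arms.

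**Sources that do not need the visit, in both arms.**
- State data (Data Collection Overview) include outpatient visits and medications: "Data extraction for secondary outcomes will occur after 180 days, which will encompass the 30-, 90-, and 180-day outcome timepoints we will report".
- Medical-record review covers outpatient treatment to 90 and 180 days (Research Material Obtained from Participants).
- A release form is signed before discharge when the planned clinic lies outside the UW system: "This process will need to be done for all participants regardless of which study condition they are assigned to".
- EHR data are collected about 30 days after enrolment (Electronic Health information).

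No section assigns any of these to the primary outcome.

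**The concern.** On the stated route, the records search starts from what the participant reports. Someone who is not reached names no setting, so there is nothing to substantiate. The analysis must still include that person, and the plan does not say how.

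The arms are unlikely to be equally easy to reach. One arm has frequent paid contact and a navigator who may also be research staff; the other has neither. One arm also has a paid reason to produce evidence of linkage. If linkage is more often detected in one arm, the risk ratio moves away from 1 with no difference in actual linkage, and an adjusted regression does not correct that. The visit window adds a smaller problem: a report taken as late as day 90 has to be dated back to a 30-day window.

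The pilot is meant to inform a larger trial, so a distorted linkage estimate, or the method that produced it, would be carried forward.

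**Working it through.** **Inputs from the documents.** 20 per arm (Involvement of Human Subjects). Expected TAU linkage of 20% to 50% (Sample Size and Power); I use 40%. The effect measure is a risk ratio (RR).

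**Assumptions.** The documents give no follow-up rates. I take 90% to 95% in MIAPP and 50% to 90% in TAU. No alpha is stated; I take two-sided 5%, in line with the planned 95% interval. True linkage is equal in the two arms throughout.

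**Scale: the plan's own figure.** There is no planned follow-up figure to reproduce. The related figure is a detectable RR of 2.05 at 40% TAU linkage. With proportions 0.40 and 0.82 (mean 0.61) and n = 20, the normal approximation gives z = (0.42 × √20 − 1.96 × √(2 × 0.61 × 0.39)) / √(0.40 × 0.60 + 0.82 × 0.18) = (1.878 − 1.352) / 0.623 = 0.845. Power is 80%, so the figure reproduces.

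**Step 1. Unreached counted as not linked, follow-up independent of linkage.** Observed linkage = true linkage × follow-up, so the apparent RR = follow-up in MIAPP / follow-up in TAU. Rejection rates come from exact enumeration with 20 per arm.

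| Follow-up, MIAPP / TAU | Observed linkage | Apparent RR | Rejection, chi-square | Rejection, Wald on log RR |
|---|---|---|---|---|
| 90% / 90% | 36% / 36% | 1.00 | 5.2% | 3.1% |
| 90% / 70% | 36% / 28% | 1.29 | 8.8% | 4.8% |
| 90% / 60% | 36% / 24% | 1.50 | 13.6% | 7.4% |
| 95% / 50% | 38% / 20% | 1.90 | 24.8% | 14.3% |

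**Step 2. Complete-case analysis.** Linkage among those reached = p·f(linked) / [p·f(linked) + (1 − p)·f(not linked)], with p = 0.40.
- TAU reaches 90% of linkers and 60% of non-linkers; MIAPP reaches 90% of both. TAU: 0.36 / (0.36 + 0.36) = 0.50. MIAPP: 0.40. RR = 0.80.
- MIAPP reaches 95% of linkers and 60% of non-linkers; TAU reaches 80% of both. MIAPP: 0.38 / (0.38 + 0.36) = 0.514. TAU: 0.40. RR = 1.28.

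If follow-up is independent of linkage within each arm, both arms show 40% and there is no bias. The direction therefore depends on who is lost.

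**Step 3. If the MIAPP-only proof were counted.** Suppose 70% attend in both arms and the proof finds a share c of linked non-attenders in MIAPP. RR = (0.70 + 0.30c) / 0.70. For c = 0.5 this is 0.85 / 0.70 = 1.21; for c = 1 it is 1.00 / 0.70 = 1.43.

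**Step 4. Effect of a common record source.** If records find a share s of linkages among non-attenders in both arms, RR = [f(M) + (1 − f(M))s] / [f(T) + (1 − f(T))s].

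| Follow-up | s = 0 | s = 0.5 | s = 0.8 | s = 1 |
|---|---|---|---|---|
| 90% / 70% | 1.29 | 0.95 / 0.85 = 1.12 | 0.98 / 0.94 = 1.04 | 1.00 |
| 90% / 60% | 1.50 | 0.95 / 0.80 = 1.19 | 0.98 / 0.92 = 1.07 | 1.00 |

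The number per arm is unchanged, so the stated power figures are unaffected.

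**The case against.** The case against is substantial.

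- **Follow-up is protected in both arms.** Visit payments are equal, the telephone is allowed, the window runs to day 90, alternate contacts are collected, and law-enforcement databases are checked for people who cannot be reached. This stands, and it may keep the difference in follow-up small.
- **The inflation of false positives is modest.** With the Wald test on the log RR, which is closer to the planned model than chi-square, the rate at 90% / 70% is 4.8%, below the nominal 5%. This stands for the test, but the shift in the estimate remains.
- **This is a pilot.** Its stated goal is development and feasibility, and 40 was not chosen for full power. This lowers the severity. The linkage comparison is nevertheless the named primary outcome.
- **Operational detail may sit in the REDCap manual.** It may, but the definition of a primary outcome belongs in the protocol or SAP.
- **Visit-independent sources exist.** They do, and a reader might infer from the visit-based route that the all-randomised analysis cannot be done. The documents do not support that: these sources could supply the outcome for all 40. As written they have gaps. The release covers the planned clinic, not a different one. EHR collection is timed from enrolment, which happens in hospital, so it may end before day 30 after discharge. The study schedule places the EMR review form at discharge only. Research Material Obtained from Participants describes the state extract as readmissions and emergency visits only, whereas Data Collection Overview includes outpatient visits and medications.

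Two other stronger readings also fail. Linkage does not rest on self-report alone, because the same sentence calls for records. And the bottle or script video is evidence for a payment; no section says that it classifies the primary outcome, so Step 3 is conditional.

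**Conclusion.** The concern holds as a gap in specification. The one stated route to the primary outcome fails for participants who are not reached, the chance of being reached and of producing evidence can differ by arm, and the plan requires everyone in the analysis without saying how the unreached are classified.

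If they count as not linked and MIAPP is better followed, the bias favours MIAPP: RR 1.29 at 90% / 70% and 1.50 at 90% / 60%, against a planned detectable RR of 2.05 at the same TAU rate. These figures rest on assumed follow-up rates, on follow-up being independent of linkage within arm, and on no other source finding any linked non-attender. A reader might infer that the bias must run towards the hypothesis; under complete-case analysis it can go either way (0.80 or 1.28 in the examples). Nor is it beyond repair, since a common record source removes most of it when recovery is high.

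This should be fixed before linkage is classified. It does not invalidate the pilot.

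**What to change.** - Define primary linkage as an outpatient MOUD visit, fill or dispensing dated within 30 days after discharge, whatever the date of the research visit.
- Seek it for all 40 from the same sources: UW EHR through day 30 after discharge, released clinic records, and the state extract. Use self-report to locate further records. Confirm that the state extract includes 30-day outpatient and medication data, and reconcile the two descriptions of it.
- Do not let MIAPP-only videos classify the primary outcome unless those same records confirm them.
- Have existing staff classify linkage from records without arm labels.
- Do not read absent claims as not linked for participants without Medicaid coverage.
- State how participants with no usable source are handled, and add best-case and worst-case sensitivity analyses. Report linkage including unsubstantiated self-report as a further sensitivity analysis.

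**Cost.** Protocol and SAP wording, and one more use of data already planned. The primary result waits for the state extract after day 180. Some undocumented linkages will be missed, possibly not equally by arm, since the navigator's care coordination could itself affect documentation.
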